Using Comparative Toxicogenomics Database to identify the top genes influenced by vitamin D supplementation in thousands of experiments. One hundred five genes with at least five documented interactions with VitD were identified. Moreover, to explore if the identified genes are sharing common pathways, Enriched Ontology Clustering for the identified genes will be performed using the Metascape (a web-based tool used for comprehensive gene list annotation and analysis resource).

In silico determination of effect of vitamin D treatment on the expression of NR3C1 and NR3C2 in monocytes, macrophages, and dendritic cells

In order to investigate the effect of VitD supplementation on the mRNA expression of NR3C1, NR3C2 and VDR, publicly available datasets (GSE52819, GSE13762, GSE56490) will be explored as they were designed to examine the global transcriptional effect of VitD supplementation on monocytes, macrophages, and dendritic cells.

In silico determination of the mRNA expression levels, and correlations, of NR3C1, NR3C2, and VDR in the blood of asthmatic patients compared to healthy controls

We will extract from publicly available datasets (GSE69683) with a large number of participants and their detailed clinical information. To find Gene expression profiling of blood from these groups was analyzed, and the gene expression of GR (NR3C1 and NR3C2) which was determined.

Patients

To do double-blinded, randomized, placebo-controlled study of VitD supplementation on 45 asthmatics with VitD deficiency will be performed. Moderate to severe asthmatics between 18 and 65 years of age who had clinician-diagnosed asthma with 25-hydroxyvitamin D3 (25 D3) level less than 20ng/mL at the screening visit will be recruited at the Rashid Hospital, Dubai, U.A.E., and the Zayed Military Hospital, Abu Dhabi, U.A.E.

mRNA expression and cytokine expression

Whole blood will be collected in PAXgene tubes (Qiagen, Germany) for the isolation of cellular RNA. Blood specimens will be assessed for mRNA expression of Glucocorticoid receptor (GR- β and

GR- α) using qRT-PCR. Bioplex multiplex immunoassay (BioRad, CA, USA) will use to assess the protein expression of IL-17A, IL-17-F, IFN- γ , IL-4, IL-5 and TNF- α in serum obtained from patients before and after treatment.

Statistical Analysis

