To validate the *in silico* findings, a double-blinded, randomized, placebo-controlled study was performed to test the effect of VitD supplementation on 45 vitamin D deficient asthmatics. Moderate to severe asthmatics between 18 and 65 years of age who were diagnosed with asthma and VitD (25D3) levels less than 20ng/mL at the screening visit were recruited at two hospitals in UAE (Rashid Hospital, Dubai, U.A.E. and Zayed Military Hospital, Abu Dhabi, U.A.E.). The patients were divided into two groups, an experimental group and a placebo group. The baseline serum levels of VitD in the experimental and placebo groups were comparable (11.74 ± 0.77 ng/mL, 12.96 ± 1.29 ng/mL, respectively). The experimental group received 50, 000 IU of VitD

oral supplementation weekly for eight weeks ¹⁹. Following treatment, a 2.84 ± 0.01 -fold increase in blood VitD D levels (33.34 ± 2.04 ng/mL) was observed (Figure 3). The level of VitD in the placebo group did not change (14.45 ± 1.61 ng/mL) (Table 1 and Figure 3). This result indicated that the regimen used was effective to correct VitD deficiency.

Table 1: Clinical characteristics of patients received vitamin D or placebo for eight weeks.

| Variable | Total | Placebo | Vitamin D |
|--|------------------|------------------|------------------|
| Total | 54 | 20 | 34 |
| Male | 19 (35%) | 4 (20%) | 15 (44%) |
| Female | 35 (64.8%) | 16 (80%) | 19 (55.8%) |
| Age (years) | 38.64 ± 1.90 | 40.60 ± 2.97 | 37.45 ± 2.48 |
| Body Mass Index | 32.27 ± 0.92 | 32.32 ± 5.52 | 32.32 ± 1.28 |
| Pre-treatment 25D₃ levels (ng/mL) | | 12.96 ± 1.29 | 11.74 ± 0.77 |
| Post treatment 25D₃ levels (ng/mL) | | 14.45 ± 1.61 | 33.34 ± 2.04 |

[figure not shown]

Figure 3: Pre-treatment and post-treatment levels of serum vitamin D (25D3) in patients who received vitamin D or placebo for eight weeks. Severe asthmatic patients with vitamin deficiency were divided into 2 groups. 23 patients received 50000 IV of Vitamin D orally over 8 weeks, while 22 patients received placebo. Vitamin D levels were measured in the blood of these patients before and after the treatment.

We next determined whether VitD supplementation affects the gene expression of steroid receptor GR- α or GR- β . Correction of VitD levels lead to a significant increase in the expression of GR- α

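### The Results give two incompatible patient counts for the randomised study: 45 (23 vitamin D / 22 placebo) in the text and Figure 3 caption, and 54 (34 / 20) in Table 1

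*Combined protocol and SAP*

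**What the plan says.** The conflict lies within the Results section on vitamin D supplementation and the GR-α receptor.

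- **Results text.** The study was done to "test the effect of VitD supplementation on 45 vitamin D deficient asthmatics". Two groups are mentioned, without sizes or an allocation ratio.
- **Figure 3 caption.** This is the only place that splits the 45 by arm: "23 patients received 50000 IV of Vitamin D orally over 8 weeks, while 22 patients received placebo".
- **Table 1.** The total row gives 54 patients, 20 on placebo and 34 on vitamin D. The sex rows use the same denominators, for example "Male | 19 (35%) | 4 (20%) | 15 (44"%).

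Table and figure are labelled as describing the same kind of patient. The table is headed "Table 1: Clinical characteristics of patients received vitamin D or placebo for eight weeks" and the figure "Pre-treatment and post-treatment levels of serum vitamin D (25D3) in patients who received vitamin D or placebo for eight weeks". The text cites both for one finding: "The level of VitD in the placebo group did not change (14.45 ± 1.61 ng/mL) (Table 1 and Figure 3"). One label does differ: the Figure 3 caption goes on to call its patients severe asthmatics, while the text describes the study population as moderate to severe.

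Materials and Methods (Patients) also has 45, but as a plan: a "placebo-controlled study of VitD supplementation on 45 asthmatics with VitD deficiency will be performed".

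No section mentions dropout, exclusions, analysis sets or missing samples. For GR-α, GR-β, their ratio and the cytokines, the readable text gives no n (the figures themselves are not shown).

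**The concern.** The number of patients in each arm is the most basic fact about a randomised comparison, and here one 25D3 result carries two denominators. A reader cannot tell how many patients were randomised, treated or analysed per arm. Nor can the reader tell whether anyone was added, left out or counted in a different arm after allocation.

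Some of those explanations would bear on whether the between-arm comparisons are still the randomised ones. Others would not. Because no n is readable for the gene-expression and cytokine outcomes, the reader cannot work out which set of patients supports them.

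**Working it through.** **Inputs.** Results text: 45. Figure 3 caption: 23 vitamin D, 22 placebo. Table 1: total 54, placebo 20, vitamin D 34; males 19 = 4 + 15; females 35 = 16 + 19; mean age 38.64 ± 1.90 (total), 40.60 ± 2.97 (placebo), 37.45 ± 2.48 (vitamin D).

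**1. Each count reproduces on its own terms.** Caption: 23 + 22 = 45. Table 1: 20 + 34 = 54. Both sums are right; the conflict is between them.

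**2. Is 54 a misprint or a reading error?** The sex rows give placebo 4 + 16 = 20, vitamin D 15 + 19 = 34, total 19 + 35 = 54. The percentages fit:

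| Row | Calculation | Printed |
|---|---|---|
| Male, total | 19/54 = 35.2% | 35% |
| Female, total | 35/54 = 64.8% | 64.8% |
| Male, placebo | 4/20 = 20.0% | 20% |
| Female, placebo | 16/20 = 80.0% | 80% |
| Male, vitamin D | 15/34 = 44.1% | 44% |
| Female, vitamin D | 19/34 = 55.9% | 55.8% |

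On the caption's arms the rows fail: 15 + 19 = 34 vitamin D patients cannot come from 23. Transposed digits in the total (45 for 54) would not alter the arm and sex counts.

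**3. The age row agrees.** Weighted mean at 34/20: (20 × 40.60 + 34 × 37.45)/54 = 38.62. At 23/22: (22 × 40.60 + 23 × 37.45)/45 = 38.99. Printed: 38.64. If ± is a standard error, which the documents do not state, the total's standard error comes to 1.904 at 34/20 and 1.920 at 23/22 (printed 1.90). Table 1 was very probably built on about 34/20.

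**4. Can losses link the two?** Going from 54 to 45, vitamin D would fall from 34 to 23, but placebo would rise from 20 to 22. Going from 45 to 54, placebo would fall from 22 to 20 while vitamin D grew. Neither set, as labelled, contains the other.

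**5. What each reading requires.**
- If both sets of arm labels are right and nobody changed arm, at least max(34, 23) + max(20, 22) = 34 + 22 = 56 patients are needed, more than either total.
- If all 45 are among the 54 and the caption is right, 22 are placebo by the caption but at most 20 by Table 1, so at least 22 − 20 = 2 carry different arm labels.
- If the 45 are among the 54 and only the caption's split is wrong, the split lies between 25/20 and 34/11 (vitamin D/placebo), and 9 patients are unaccounted for.
- If 54 is the true count and the text and caption are slips, nobody is missing or moved.

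**6. Same result, two denominators.** The 25D3 means in the text (11.74, 12.96, 33.34 and 14.45 ng/mL) are identical to those in Table 1.

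**The case against.** The strongest reply is that this may be a plain reporting slip: the planned 45, with a near-equal split, was carried into the results text and caption while 54 patients were actually randomised and analysed. The documents do not exclude this, and the age row makes Table 1 look internally sound. This stands as a possible cause. It does not remove the contradiction, and it does not prove that 54 is the true number randomised.

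It is also fair that the 45 in Materials and Methods is only a planned number. Enrolling 54 against a plan of 45 is not in itself a contradiction and does not by itself break randomisation. The conflict is among the Results text, Table 1 and the Figure 3 caption.

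The caption's reference to severe asthmatics might suggest that Figure 3 shows a subset of Table 1. That fails, because a subset of 20 placebo patients cannot contain 22.

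Two stronger inferences are tempting and are not supported:

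- **That randomisation was broken.** Omission or relabelling of patients would bear on it; a slip in the text and caption would not. Nothing in the documents chooses between them.
- **That the reported p<0.05 for GR-α between arms is wrong.** Reading 5.34 ± 1.40 versus 1.64 ± 0.76 as standard errors with every patient contributing, a pooled t-test gives p = 0.027 at 23/22 and 0.060 at 34/20. A Welch test gives 0.026 and 0.024. The meaning of ±, the t-test variant and the number contributing are all unstated. The printed age mean would also fit 33/20, (20 × 40.60 + 33 × 37.45)/53 = 38.64, so some values may be missing.

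**Conclusion.** Wrong as written: the Results report incompatible counts for one study. The totals differ by 9 (54 versus 45; 9/54 = 17%), vitamin D by 11 (34 versus 23) and placebo by 2 the other way (20 versus 22). The arm ratio is 34/20 = 1.7 in Table 1 and 23/22 = 1.05 in the caption. Swapped digits, dropout and a severe-only subset do not reconcile them.

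This rests only on printed counts and addition, and on the two captions and the joint citation referring to the same patients. Which count is right, and why they differ, cannot be settled from the documents. The finding concerns traceability of the counts.

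**What to change.** Reconcile the counts against the allocation records. Correct the results text, Table 1 and the Figure 3 caption to the true numbers randomised and analysed per arm. Give n per arm for 25D3, GR-α, GR-β, their ratio and each cytokine. Account for any patient added, excluded or moved after allocation.

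Re-analysis is conditional. If the records show that patients were excluded, were counted in an arm other than the one allocated, or that a wrong count entered the tests, re-run the between-arm tests with all randomised patients who have data, in their allocated arm. If the slip is only in the reporting, correcting it is enough.

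The cost is a records check and corrected text, with existing tests repeated only if needed. No new data are required. The downside is that a reported p-value may become less favourable. The documents do not describe the allocation records, so their availability is an assumption.

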Steroid resistance, as documented in cases of severe asthma, is associated with increased expression of the glucocorticoid receptor (GR)- β , which is an alternative splicing isoform and dominant-negative regulator of the GR- α ¹⁴. The abundance of GR- α mRNA is higher than GR- β mRNA in all normal tissues and cells. Normally, default splicing pathway leads to GR- α , while the alternative

splicing pathway that leads to GR- β is minimally activated ¹⁵. The latter pathway, however, seems to be upregulated in severe asthmatic patients ¹⁶. In chronic inflammatory diseases like asthma, upregulated blood levels of inflammatory cytokines can participate in glucocorticoid resistance and impaired GR function by modulating its translocation, DNA binding, and GR phosphorylation status [18].

As data from observational studies suggested a better control of asthma following restoration of VitD levels.

Hypothesis:

Correcting VitD levels in adult asthmatic patients could enhance steroid responsiveness by regulating blood GR- α /GR- β ratio levels.

Primary Out comes:

1. To find out the top pathways regulate Vitamin D

identify VitD targeted enriched pathways, we analyzed Comparative Toxicogenomics .Enriched Ontology Clustering for the identified genes was performed using the Metascape (a web-based tool used for comprehensive gene list annotation and analysis resource)Database from thousands of experiments.[Time Frame: 8 weeks]

2. To examine asthma severity in relation to steroid receptors genes [Time Frame: 8 weeks]

3. study the effect of vitamin D on GR- α receptor [Time Frame: 8 weeks]

4. study the effects of Vitamin D on cytokines. [Time Frame: 8 weeks]

Inclusion Criteria:

- Diagnosis of asthma
- age group between 18 and 65 years
- low level of 25-hydroxyvitamin D3 (25 D3) level less than 20ng/mL

Exclusion Criteria:

- smoker patients
- less than 18 years old
- patient on Vitamin D supplementation already

Materials and Methods

In silico identification of top genes regulated by vitamin D supplementation

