Standard statistical t-tests and one-way ANOVA will be performed to test for statistical significance between data groups using GraphPad Prism 8 (GraphPad, San Diego, CA, USA). $p < 0.05$ was considered significant.

To whom it may concern

Date : 15/06/2020

Subject : Vitamin D Regulates the Expression of Glucocorticoid Receptors in Blood of Severe Asthmatic Patients

I am [name] ,Principle investigator for the study (Vitamin D Regulates the Expression of Glucocorticoid Receptors in Blood of Severe Asthmatic Patients) . I am confirming that the results is relevant to the study in the record.

Results :

Top Vitamin D regulated pathways are involved in response to Steroids

To identify VitD targeted enriched pathways, we analyzed Comparative Toxicogenomics Database from thousands of experiments. Interestingly, the top enriched pathways regulated by VitD were involved in several metabolic and inflammatory processes including response to steroids, lipopolysaccharide as well as Interleukin-4, Interleukin-13 and AGE-RAGE signalling (Suppl. Figure 1). Many of those VitD targeted pathways were also targets of dexamethasone. These include pathways involved in inflammation; proliferation; pro-apoptosis, beside others (Figure S1).

VDR, NR3C1 and NR3C2 expression levels in different types of immune cells

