when compared to baseline level. A significant increase was observed following treatment with VitD compared to pre-treatment levels (1.89 ± 0.56 , 5.34 ± 1.40 , respectively; $p<0.05$) (Figure 4A). Moreover, there was a significant increase in GR- α expression in patients who received VitD compared to those who received the placebo control (5.34 ± 1.40 versus 1.64 ± 0.76 -fold; $p<0.05$). Interestingly, no change in GR- β expression was observed following treatment with VitD (1.49 ± 0.27 versus 1.30 ± 0.25) (Figure 4B). Relatively, the GR- α /GR- β ratio increased significantly following VitD supplementation compared to pre-treatment levels (3.58 ± 0.83 folds; $p<0.05$); or patients who received a placebo (Figure 4C).

[figure not shown]

Figure 4: Vitamin D treatment increases the expression of GR- α with no effect on GR- β .

Asthmatic subjects were treated with 50,000 IU of vitamin D orally or placebo for eight weeks. Blood specimens obtained following 8 weeks of treatment were analyzed for mRNA expression of GR- α (A), GR- β (B) using RT qPCR and the ratio of GR- α /GR- β was calculated (C). * $p<0.05$

Vitamin D supplementation downregulated the blood levels of IL-17 and IL-4 cytokines in asthmatic patients

The effect of VitD supplementation on the blood levels of asthma related pro-inflammatory cytokines was then determined (Figure 5)²⁰. Blood levels of IL-17A, IL-17F, IFN- γ , IL-4, IL-5, and TNF- α were determined before and after VitD supplementation using ELISA assay (Figure 5). VitD preferentially suppressed the blood levels of IL-17F cytokine ($p=0.04$) without affecting IL-17A; while there was no significant difference in the placebo group ($p=0.17$). A decrease in blood IL-4 cytokine levels was observed following treatment, however, not to a significant level ($p=0.07$). No significant effect of VitD supplementation was observed on the rest of the cytokines tested.

References

- 1 Palacios, C. & Gonzalez, L. Is vitamin D deficiency a major global public health problem? *J Steroid Biochem Mol Biol* **144 Pt A**, 138-145, doi:10.1016/j.jsbmb.2013.11.003 (2014).

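### GR-α, one of four primary outcomes, is reported and apparently t-tested as arithmetic mean qPCR folds; if the unlabelled ± is SEM, the SD exceeds the mean in all three reported cells, and the analysis belongs on the delta-Ct (log2) scale

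*Combined protocol and SAP*

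**What the plan says.** The list of primary outcomes has four entries, of which the third is to "study the effect of vitamin D on GR- α receptor [Time Frame: 8 weeks". The stated hypothesis concerns the GR-α/GR-β ratio. The section on mRNA and cytokine expression says the two receptor isoforms are assessed by qRT-PCR, without naming a reference gene, a calibrator or a formula for the fold.

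The Statistical Analysis section reads "Standard statistical t-tests and one-way ANOVA will be performed to test for statistical significance between data groups using GraphPad Prism 8" and adds only the 0.05 significance threshold. It mentions no transformation, distribution check or rank-based alternative.

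The Results section on GR-α gives, within the vitamin D arm, "A significant increase was observed following treatment with VitD compared to pre-treatment levels (1.89 ± 0.56 , 5.34 ± 1.40 , respectively", and between arms "compared to those who received the placebo control (5.34 ± 1.40 versus 1.64 ± 0.76 -fold". Both comparisons are printed as p<0.05. The same section gives GR-β as 1.49 ± 0.27 versus 1.30 ± 0.25 and a GR-α/GR-β ratio of 3.58 ± 0.83. The ± is not labelled, n per cell is not given, and the placebo baseline for GR-α is not reported. Arm sizes are 23 vitamin D and 22 placebo in the Figure 3 legend, but 34 and 20 in Table 1. The public array data in the same report are given as log2 intensity.

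**The concern.** A qPCR cycle threshold is already a log2 quantity. Converting it to a linear fold and averaging gives most weight to the highest values. With a wide spread, the arithmetic mean no longer describes a typical patient, a few patients carry much of the total, and a t-test on that scale is inefficient.

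The GR-α contrast is the trial's evidence on one primary outcome and feeds the ratio in the hypothesis. The ratio needs the same care. A quotient of two group means is not the average of patients' own ratios, and it is the patient's own ratio that the hypothesis is about.

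**Working it through.** **Inputs.** GR-α: pre-treatment 1.89 ± 0.56, post-treatment 5.34 ± 1.40, placebo 1.64 ± 0.76 (Results). Arm sizes: 23/22 (Figure 3 legend) or 34/20 (Table 1). Age: total 38.64 ± 1.90, placebo 40.60 ± 2.97, vitamin D 37.45 ± 2.48 (Table 1). Sidedness is not stated; two-sided tests are assumed.

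**1. What ± means in the age row.** Read as SEM at 34/20, the arm SDs are 2.48 × √34 = 14.46 and 2.97 × √20 = 13.28. The combined mean is (34 × 37.45 + 20 × 40.60)/54 = 38.62. The combined variance is [33 × 14.46² + 19 × 13.28² + 34 × (37.45 − 38.62)² + 20 × (40.60 − 38.62)²]/53, so the total SD is 13.99 and the SEM is 13.99/√54 = 1.904. Table 1 prints 1.90. Read as SDs, the total would be 3.06. In that row ± is SEM.

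**2. The printed significance, raw fold scale, ± as SEM.**
- Post-treatment versus placebo: (5.34 − 1.64)/√(1.40² + 0.76²) = 2.32 (Welch). At 23/22, p = 0.026; the pooled test gives t = 2.29, p = 0.027.
- Post versus pre, 23 patients: (5.34 − 1.89)/√(1.40² + 0.56²) = 2.29. Unpaired p = 0.027; paired p = 0.032 to 0.010 for a within-patient correlation of 0 to 0.5.
- Post versus placebo at 34/20: Welch p = 0.024, but pooled t = 1.93, p = 0.060.

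The printed p<0.05 is reproduced at 23/22 by either test, and at 34/20 by Welch only. With ± read as SD at 23/22, t is about 11 and p is below 10⁻¹².

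**3. Implied spread, SD = SEM × √n.**

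| Cell | Mean | SD (CV), 23/22 | SD (CV), 34/20 | CV if ± is SD |
|---|---|---|---|---|
| Vitamin D, pre | 1.89 | 2.69 (142%) | 3.27 (173%) | 30% |
| Vitamin D, post | 5.34 | 6.71 (126%) | 8.16 (153%) | 26% |
| Placebo | 1.64 | 3.56 (217%) | 3.40 (207%) | 46% |

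Under SEM, the SD exceeds the mean once n > (mean/SEM)², that is from n = 12, 15 and 5 respectively, so the result does not depend on which arm sizes are right. A normal curve with these values would put 21% to 32% of patients below zero, which a fold cannot be.

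**4. The ratio.** 5.34/1.49 = 3.58, the printed GR-α/GR-β ratio. A mean of per-patient ratios would not in general equal this quotient.

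**5. Size of the loss (illustration only).** Assume log-normal folds, with median = mean/√(1 + CV²). At 23/22 the typical values are about 3.3 (post), 1.1 (pre) and 0.7 (placebo). In simulated samples of 23 with the post-treatment moments, the top three patients hold about 40% of the total (median over samples). Simulated power for a true 2-fold difference, with equal CV in both arms, two-sided 0.05 and 20,000 trials:

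| Setting | Raw folds | log2 |
|---|---|---|
| 23/22, CV 126% | 47% | 64% |
| 34/20, CV 153%, Welch | about 49% | about 59% |
| 34/20, CV 153%, pooled | 32% | 60% |

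Most of the gap in the last row comes from pooling variances with unequal arms, so the Welch row is the fair measure of the scale effect at 34/20.

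**The case against.** **The two key steps are inferences.** The ± is unlabelled, and the documents do not say that the tests were run on the folds; folds can be displayed while tests are done on another scale. The meaning of ± also varies in this report. Placebo BMI (± 5.52) looks like an SD. The NR3C1 array figures behave as SDs too: 0.23 and 0.21 with 246 and 77 patients give p of about 0.00006, printed as p<0.01. This stands, and it makes the skew argument conditional.

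**A reader might infer that only SEM fits a p just under 0.05.** The documents print a threshold, not a p-value, and the array example shows that a threshold can sit far above the actual p. In addition, the age row matches SEM best at 34/20, where the pooled test gives 0.060. The SEM reading is well supported but not proved.

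**A reader might infer that a few high responders created the GR-α result.** The documents do not support that. Under the log-normal model with no effect, raw-fold tests reject about 4% of the time, slightly below nominal. The vitamin D/placebo ratio under that model is about 4.8 (23/22), above the arithmetic 5.34/1.64 = 3.3. So the individual folds may shrink while the contrast grows. That figure comes from the assumed distribution, not from trial data.

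**Scope is limited.** The SD-above-mean finding covers the three reported GR-α cells. It does not extend to GR-β at n = 23 (SD 1.29 against mean 1.49; 1.20 against 1.30). The quotient match for the ratio is also only suggestive: the printed ± 0.83 may come from per-patient values.

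**Conclusion.** The point holds conditionally, with moderate confidence. The certain part is that a primary outcome measured by qPCR is reported as arithmetic mean folds, and that the plan gives no delta-Ct derivation, analysis scale, meaning of ± or n per cell.

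The conditional part assumes that ± is SEM and that the tests used the folds. GR-α is then strongly right-skewed under either set of arm sizes, 5.34 overstates the typical post-treatment value (about 3.3 at 23/22 if log-normal), and the raw-scale test gives up about 17 points of power at 23/22 or about 10 at 34/20 by Welch. The power figures also assume equal CVs, although the implied CVs differ between arms. If ± is SD, the skew argument does not hold.

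At 34/20 with ± as SEM, significance at 0.05 turns on an unstated choice between pooled and Welch tests. This is fragility, not evidence of a false positive; a log2 analysis could strengthen or weaken the contrast.

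**What to change.** In the Statistical Analysis section:

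- Derive GR-α and GR-β for each patient and visit as delta-Ct against a named reference gene.
- Derive the GR-α/GR-β ratio per patient as the difference of the two delta-Ct values.
- Run all tests on that log2 scale and name the test variant.
- Report geometric mean fold ratios with 95% intervals, against one stated calibrator for all samples. The pre-treatment mean of 1.89 shows that the calibrator is not simply each patient's own baseline.

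In the Results text and Figure 4, replace arithmetic fold ± error with these summaries. Label ± throughout, give n per cell, and reconcile 23/22 with 34/20. The sponsor should also confirm on which scale the reported tests were run.

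The cost is a few sentences and a re-analysis of the Ct values, which the assay yields but the documents do not show. No new samples are needed. The reported fold figures may change in either direction.

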Activated T cells was shown to upregulate VDR, while treatment with VitD suppressed the proliferation of these cells, as well as their ability to produce IFN- γ and IL-17 cytokines.¹⁸ The level of expression of VDR in the blood of asthmatic and its association with the expression of steroid receptors relative to disease severity was not determined. To investigate that, we analyzed the expression profile of publicly available datasets (GSE69683) which has a large number of participants and detailed clinical information. A total number of 498 participants, of which 87 healthy controls, 77 moderate asthma, and 246 non-smokers severe asthma were included in the U-BIOPRED study. The differential expression of NR3C1, NR3C2, and VDR genes in the blood of patients from all groups was then determined. Patients with moderate asthma had higher levels of NR3C1 mRNA expression compared to health controls, although not to a significant level (\log_2 intensity 10.17 ± 0.29 ; $p=0.07$) (Figure 2A). When compared to moderate asthmatics, the expression of this gene, however, was significantly downregulated in severe asthmatic (\log_2 intensity 10.14 ± 0.23 versus 10.26 ± 0.21 ; $p<0.01$). NR3C2 mRNA expression was significantly downregulated in severe asthmatic compared to moderate asthma (\log_2 intensity 5.397 ± 0.727 versus 5.62 ± 0.5011 , $p<0.01$), and to healthy controls (\log_2 intensity 5.575 ± 0.5894 versus 5.397 ± 0.727 , $p=0.03$) (Figure 2B). Moderate asthmatics showed higher NR3C2 mRNA expression than healthy controls, although the difference was not significant. On the other hand, VDR mRNA expression was significantly upregulated in severe asthmatics compared to healthy controls (\log_2 intensity 8.386 ± 0.46 versus 8.206 ± 0.44 $p<0.01$), but not to moderate asthmatics (Figure 2C). Interestingly, NR3C1 mRNA expression correlated positively (Spearman $r = 0.11$, 95% confident interval=0.02007 to 0.1988 and $p = 0.01$) (Figure 2D), while NR3C2 expression correlated

negatively (Spearman $r = -0.55$, 95% confident interval = -0.5724 to -0.438 and $p < 0.0001$) with the levels of VDR expression in blood (Figure 2E).

[figure not shown]

Figure 2: NR3C1, NR3C2 and VDR mRNA expression level in the blood of subjects with severe asthma, moderate asthma, and non-asthmatics. Data was collected in the U-BIOPRED study (GSE69683).

Supplementation of vitamin D selectively favours the upregulation of GR- α receptor

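### GR-β is reported as unaffected by vitamin D, but the printed figures do not exclude a sizeable change, and the ratio result offered for selectivity is incompletely reported

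*Combined protocol and SAP*

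**What the plan says.** All the statements at issue stand in the Results part of the combined protocol and SAP, in the section headed "Supplementation of vitamin D selectively favours the upregulation of GR- α receptor".

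- **GR-α over time (vitamin D arm):** "1.89 ± 0.56 , 5.34 ± 1.40 , respectively; $p<0.05".
- **GR-α against placebo:** "5.34 ± 1.40 versus 1.64 ± 0.76 -fold; $p<0.05".
- **GR-β:** "no change in GR- β expression was observed following treatment with VitD (1.49 ± 0.27 versus 1.30 ± 0.25"). No p-value, interval or margin follows, and the second number is not labelled.
- **Ratio of GR-α to GR-β:** "ratio increased significantly following VitD supplementation compared to pre-treatment levels (3.58 ± 0.83 folds; $p<0.05$); or patients who received a placebo", with reference to Figure 4C.
- **Figure 4 caption:** "Vitamin D treatment increases the expression of GR- α with no effect on GR- β".

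The Statistical Analysis section plans t-tests and one-way ANOVA at the 0.05 level. It plans no equivalence test. The Hypothesis is framed on the GR-α/GR-β ratio, and the third listed primary outcome is the effect on GR-α.

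**The concern.** A comparison that does not reach significance leaves open every value inside its confidence interval. It supports a statement of no effect only if that interval is narrow against some stated margin. Here there is neither an interval nor a margin, yet the text moves from no change to no effect.

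The Introduction describes GR-β as a dominant-negative regulator of GR-α and links its increased expression to steroid resistance. A rise in GR-β under vitamin D would therefore bear directly on the proposed mechanism. If the data cannot exclude such a rise, a reader who takes the caption at face value is told more than the trial found.

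The heading adds that the action is selective. That is a claim about the two isoforms relative to each other, so it depends on how well the ratio result is reported.

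**Working it through.** **Inputs.** Means and ± values come from the Results section on GR-α and GR-β. The Figure 3 caption gives 23 vitamin D and 22 placebo patients, while Table 1 gives 34 and 20. These must be reconciled, so both are used. Tests are taken as two-sided at 0.05, since sidedness is not stated. The pre/post correlation r is not reported and is varied from 0 to 0.8.

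**Step 1: what ± means.** The documents do not say. Read as a standard error (SEM), the GR-α figures give:
- Pre/post: SE = √(0.56² + 1.40²) = 1.508; t = (5.34 − 1.89)/1.508 = 2.29; p = 0.03.
- Against placebo: SE = √(1.40² + 0.76²) = 1.593; t = (5.34 − 1.64)/1.593 = 2.32; p = 0.026.

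Both agree with the stated p<0.05. Read as an SD with n = 23, the pre/post t would be about 11, which is hard to match with a result reported only as p<0.05. Age in Table 1 points the same way: 37.45 ± 2.48 as SEM with n = 34 implies an SD of 2.48 × √34 = 14.5, whereas an SD of 2.48 is implausible for adults aged 18 to 65. One entry does not fit: the placebo body mass index of 32.32 ± 5.52 would imply an SD of 5.52 × √20 = 24.7 if 5.52 were an SEM. The SEM reading therefore remains an assumption.

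**Step 2: GR-β interval with 1.30 as the pre-treatment value.** Difference = 1.49 − 1.30 = 0.19, and 0.19/1.30 = 15%. SE = √(0.27² + 0.25² − 2r × 0.27 × 0.25). The 95% CI is 0.19 ± 2.074 × SE (t with 22 df, n = 23).

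| r | SE | p | 95% CI | As % of 1.30 |
|---|---|---|---|---|
| 0 | 0.368 | 0.61 | -0.57 to 0.95 | -44% to +73% |
| 0.5 | 0.261 | 0.47 | -0.35 to 0.73 | -27% to +56% |
| 0.8 | 0.166 | 0.26 | -0.15 to 0.53 | -12% to +41% |

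With n = 34 the rows become -43% to +72%, -26% to +55% and -11% to +41%.

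**Step 3: 1.30 as the placebo value.** The groups are then independent, with SE 0.368 and about 43 df. The 95% CI is -0.55 to 0.93, or -42% to +72% of 1.30.

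**Step 4: fold scale.** The ratio of means is 1.49/1.30 = 1.15. At r = 0, SE(log) = √((0.27/1.49)² + (0.25/1.30)²) = 0.264, and the 95% CI is 0.66 to 1.98. At r = 0.5 it is 0.78 to 1.69.

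**Step 5: the SD reading.** With n = 23 per set, SE = √(0.27²/23 + 0.25²/23) = 0.077, t = 2.48 and p = 0.017 (unpaired). The 95% CI is 0.04 to 0.34. On that reading GR-β would have differed significantly, so no change would fail for a different reason.

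**Step 6: the ratio.** 5.34/1.49 = 3.58, which is the printed value. It therefore matches a post-treatment level. If 1.30 is the pre-treatment GR-β value, the pre-treatment ratio of means is 1.89/1.30 = 1.45, and the change is 3.58/1.45 = 2.47-fold. Treating the two isoforms as independent (SEM, n = 23), the 95% CI for this change is 0.92 to 6.61 (p = 0.07) at r = 0 and 1.22 to 4.96 (p = 0.014) at r = 0.5. The printed means alone do not settle significance. Patient-level ratios could.

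**The case against.** **Selectivity has its own test.** A reader might infer that the authors called the effect selective only because GR-α was significant and GR-β was not, and hence that selectivity is not shown. The documents do not support that. The sentence after the GR-β result reports a significant rise in the GR-α/GR-β ratio from pre-treatment and states a rise against placebo. A test on the ratio is the right kind of evidence for a relative claim. This objection stands. What remains is that the result is incompletely reported: 3.58 matches a level, and the placebo comparison has no figures. The label of folds does not settle the matter, since the GR-α levels carry the same label.

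**A placebo comparison may exist.** A reader might also infer that GR-β was only compared over time. The text does not establish this. The preceding sentence uses the same form to compare vitamin D with placebo, so 1.30 may be the placebo value, and Figure 4B, which was not available for this check, may show the comparison. This stands too, but Step 3 gives nearly the same interval as r = 0.

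**The correlation may be high.** That would narrow the paired interval. Even at 0.8 it reaches +41%.

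**Importance.** Neither the GR-α outcome nor the ratio hypothesis requires GR-β to be unchanged, and the ratio would capture a modest rise in GR-β. That limits the weight of the point without rescuing the caption, which makes a separate claim about GR-β.

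**The remedy goes beyond the plan.** The Statistical Analysis section names only t-tests and ANOVA, and no baseline GR value is printed for the placebo arm. Both limits are accepted in the fix.

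**Conclusion.** The statement that vitamin D has no effect on GR-β is not shown. Under the SEM reading with n = 23, the figures are compatible with anything from a fall of about 44% to a rise of about 73% at correlation 0, and from a fall of about 12% to a rise of about 41% at 0.8. The unlabelled comparator and the conflicting group sizes barely alter this. If ± were an SD, the difference would be significant, so the wording fails on either reading.

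The GR-α result is not in question. Nor do the documents support the stronger conclusion that selectivity is refuted or untested, because a ratio test is reported. Selectivity is best described as claimed on a ratio result that cannot be verified from what is printed.

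The conclusion rests on two-sided 0.05 tests, ± as SEM and assumed correlations from 0 to 0.8. The size of the interval depends on these assumptions. The absence of any interval or margin in the text does not.

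**What to change.** 1. State whether 1.30 is the pre-treatment or the placebo value, whether ± is SEM or SD, and how many patients enter each comparison (reconciling 23/22 with 34/20).
2. In the GR-β sentence and the Figure 4 caption, replace the claims of no change and no effect with no significant change, provided the clarified analysis confirms it. Beside it, give the between-arm difference in GR-β at 8 weeks on the log scale with its 95% CI. Adjust for baseline where baseline GR-β is available in both arms.
3. Report the between-arm difference in patient-level log(GR-α/GR-β) with its 95% CI, and state whether 3.58 is a level or a change. Keep the word selectively in the section heading only if that result supports it.
4. Identify the analyses in 2 and 3 as post hoc, since the Statistical Analysis section names only t-tests and ANOVA.

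**Cost.** A small added analysis of the GR-α and GR-β assays that the protocol plans, a few reworded lines, and a more cautious claim. If placebo baseline values were not measured, the GR-β comparison is made at 8 weeks without adjustment and will be less precise.
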